6.2 PREPARATION/HANDLING/STORAGE/ACCOUNTABILITY

6.2.1 ACQUISITION AND ACCOUNTABILITY

The PICO VR headsets loaded with the EaseVRx software programs will be provided by AppliedVR. The devices will be managed by the research team at Cedars-Sinai Medical Center.

6.2.2 FORMULATION, APPEARANCE, PACKAGING, AND LABELING

N/A

6.2.3 PRODUCT STORAGE AND STABILITY

The PICO VR headsets will remain in the boxes supplied by AppliedVR until they are shipped to participants.

6.2.4 PREPARATION

Prior to shipping a VR headset to a study participant, the headset battery will be checked to make sure it is fully charged. Any headsets that are handled by staff will be sanitized by cleaning the fabric surfaces using Virex, the plastic housing using Sani-Wipes, and the glass lenses using alcohol-based lens cleaner.

The group that gets the PainTRAINER program will be mailed a user's guide.

6.3 MEASURES TO MINIMIZE BIAS: RANDOMIZATION AND BLINDING

We will allocate study participants using a random number generator to assign every-other patient to blocks of 2, 5, or 6 to ensure there is an equal distribution in the EaseVRx skills-based group and PainTRAINER group. Participants, their clinical providers, and study statisticians will be blinded to the study arm. The groups will be labeled as 1 or 0 at random. Datasets will be provided to the statistician using these group labels. A clinical research coordinator will ship VR headset containers to participants in the EaseVRx group and enter the label into the log of enrolled participants; the research coordinator who maintains the list of randomization assignments will not call participants on the telephone. Because the intervention is conducted in participants' homes and the data are collected remotely, the participants will not encounter each other and thus will be less likely to guess their study arm assignment. We anticipate there will be no circumstances during the study that require unblinding of an individual participant or a whole group because we do not expect any related SAEs to occur with this low risk intervention.

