1.2 SCHEMA

1.3 SCHEDULE OF ACTIVITIES (SOA)

Procedures	Baseline / Screening	Day 1 of Week 1	8-Week Intervention									Post Intervention
	0	1	1	2	3	4	5	6	7	8	9	
Week	0	1	1	2	3	4	5	6	7	8	9	12
Prospective patients identified (Cohort Builder or Provider)	X											
Informed consent in person or over phone	X											
Verify eligibility in chart review or from [name]:	X											
• Medical history												
• Demographics												
Randomization	X											
Baseline Questionnaires (Listed below with)	X											
Shipment of VR device and/or study documents	X											
Technical onboarding call		X										
Milligram Morphine Equivalent (MME) Daily Dose	X										X	
Return of VR Device												X
Deliver honorarium						X					X	X
Self-Reported Questionnaires												
NIH developed baseline demographics, biological sex	X (Day 1)											
Daily Pain Medications Used	X										X	
Daily Pain Intensity	X										X	
Pain Catastrophizing Scale	X (Day 4)		X	X	X	X	X	X	X	X	X	
PROMIS Anxiety Scale	X (Day 4)		X	X	X	X	X	X	X	X	X	
PROMIS Pain Interference Scale	X (Day 4)		X	X	X	X	X	X	X	X	X	
The Pain Self-Efficacy Questionnaire (PSEQ) 2-item short form	X (Day 4)		X	X	X	X	X	X	X	X	X	
Simulator Sickness Questionnaire (VR Only)		X										
Treatment Usage Questionnaire			X	X	X	X	X	X	X	X	X	X
Events Assessment			X	X	X	X	X	X	X	X	X	
Custom Questions		X									X	
Treatment Expectation	X (Day 4)	X										
Concomitant Procedures Questionnaire	X (Day 4)										X	
Primary Pain Questionnaire											X	
Coping with Weekly Pain Questionnaire	X (Day 7)										X	X

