4 STUDY DESIGN

4.1 OVERALL DESIGN

We will perform a two-arm RCT among a geographically diverse group of patients with mixed-etiology chronic pain. Using a random number generator, patients will be allocated in a 1:1 ratio at the site level between two self-administered, remotely deployed CBT delivery platforms: (1) a 2D mHealth app called PainTRAINER; and (2) 3D VR app called EaseVRx. The primary analysis will compare changes in pain intensity over 8 weeks upon completion of the standardized 8-week digital CBT protocols. Secondary outcomes will include pain catastrophizing, pain interference, self-efficacy, anxiety, and opioid use. Patient blinding is not possible in VR versus non-VR studies; we will explain the purpose of our study is to determine if one of two self-taught pain-management skills programs is more effective in helping manage pain, alongside current treatment. If so, how much more effective is it and which patients does the program help the most? Both programs have been proven effective; in other words, both programs have been studied and results for both showed improvement in patients' ability to manage their pain. To do this, participants will be randomly assigned to test either a virtual reality (VR) program called EaseVRx or an online/mobile program called painTRAINER. Because it is important for researchers to exhibit equipoise when describing the competing interventions, we will prepare a script that uses neutral language regarding the two interventions, as per previous VR research. In addition, data analysts will be blinded to patient allocation.

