- **Post-Consent:** A copy of the informed consent documents will be provided to the participants for their records via email, and via postal service if no email is available. Participants will consent remotely and those randomized to the VR arm will receive their study equipment through a secure FedEx package. Study participants will receive their study equipment or documentation through secure FedEx package delivery. Retention to the 12-week study will be managed using protocolized reminder calls, emails, and/or SMS text messages to complete the study surveys. Study coordinators will contact the participant following non-completion of a survey if >1 week has elapsed since the initial survey send date. The study coordinator will employ a Tableau dashboard that provides protocol adherence data to guide contact decisions.
- Participants who complete the consent form will be required to finish the baseline questionnaires in order to be randomized and have the study equipment shipped to them as described above. Participants will be emailed tracking information and, if randomized into the VR arm, videos describing use of the intervention.
- Participants will be called for study onboarding once the VR device or painTRAINER workbook is delivered to their home. During this call, patients will be asked if they reviewed the startup instructions that were provided in the intervention tracking information email, and coordinators will answer any remaining questions and guide participants through the device or program if necessary. If participants are unreachable by phone, study staff will seek to schedule a phone call or confirm the participant's understanding of study procedure by email, or by patient prior to initiation of study surveys. Contact information will be provided for technical support throughout the participant's study enrollment.

This protocol is not high risk for subject attrition; the intervention itself is considered low risk by our IRB.

Strategies for retention include the following:

- During the recruitment process, subjects will be educated about the importance of their role in contributing to research, to increase the likelihood that they will complete the patient reported outcome measures even if they stop using the intervention.
- Participants will be educated on how to use PainTRAINER or VR via educational videos, talking with study staff, and referring to any applicable documentation.

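### Section 6.3 claims participant blinding that 4.1 rules out, and describes a blocking scheme that cannot guarantee the equal split it promises

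*Combined protocol and SAP*

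**What the plan says.** **Allocation.** Section 4.1 uses a random number generator and says "patients will be allocated in a 1:1 ratio at the site level". Section 6.3 describes the method as "using a random number generator to assign every-other patient to blocks of 2, 5, or 6 to ensure there is an equal distribution" between the two groups. It does not mention site and does not say how the odd seat in a block of 5 is filled.

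**Blinding.** Section 6.3: "Participants, their clinical providers, and study statisticians will be blinded to the study arm". It supports this by arguing that, since the trial is run remotely, "the participants will not encounter each other and thus will be less likely to guess their study arm assignment". It also foresees no circumstance that would require unblinding a participant. Section 4.1: "Patient blinding is not possible in VR versus non-VR studies". The same section says "participants will be randomly assigned to test either a virtual reality (VR) program called EaseVRx or an online/mobile program called painTRAINER", and promises that data analysts will be blinded.

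**What participants receive.** Under 6.3 headsets are shipped to the EaseVRx group, and under 6.2.4 the other group is mailed a user's guide. Section 5.5: "Participants will be called for study onboarding once the VR device or painTRAINER workbook is delivered to their home".

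**What statisticians see.** Section 6.3 gives them datasets with arms labelled 1 or 0. The Schedule of Activities lists the Simulator Sickness Questionnaire (SSQ) for the VR arm only. Under 10.1.7 the statisticians prepare monthly reports on forms completed or missing, and under 6.4 they decide whether surveys completed out of order are usable.

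**The concern.** The two sections cannot both be right about participant blinding. The primary outcome is self-reported pain intensity, so knowing one's arm can influence the rating directly. A report that repeats 6.3 would tell readers that this route to bias was closed when it was open.

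The allocation sentence does not define one sequence. It promises equality with a block size that cannot deliver it, and one of its phrases can be read as alternation. Under alternation every assignment after the first would be known in advance. What is at stake is whether readers can judge predictability and selection, and whether the site structure of 4.1 was used. Sample size is not at stake.

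**Working it through.** **1. The plan's own power figures (9.2).** Inputs: 150 per arm, SD 2, difference 0.75, two-sided alpha 0.05.

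- Means: 0.75 / (2 × √(2/150)) = 0.75 / 0.2309 = 3.248. Then 3.248 - 1.960 = 1.288, so power = Φ(1.288) = 0.901. The stated 90% reproduces.
- Response rates: control 0.30, odds ratio 2.17 (Table 1, R² = 0). The other rate is 0.30 × 2.17 / (0.70 + 0.30 × 2.17) = 0.651 / 1.351 = 0.482. The pooled two-proportion formula at 150/150 gives 0.9015, so this also reproduces.

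**2. Can the blocks ensure equality?** Blocks of 2 and 6 split 1:1 and 3:3. A complete block of 5 splits 3:2 at best, that is 60% and 40%. Equality is possible over the whole trial but is not ensured.

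**3. Size of the imbalance at N = 300.** Assumptions that the documents do not supply: block sizes equally likely, and four sites of 75.

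| Scheme | Arm difference |
|---|---|
| 2/5/6, odd seat random | SD about 5.3; 95% range -10 to +10; about 3% of trials beyond 10; simulated maximum about 20 |
| 2/5/6, odd seat always to the same arm | mean about 23, i.e. roughly 162 v 138 |
| Even blocks 4/6/8 | 95% range -4 to +4 |

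The fixed-seat figure agrees with direct arithmetic: (1 + 3 + 3) / 13 × 300 = 161.5.

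**4. Effect on power.**

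| Split | Response rates, 0.30 v 0.482 | Means, 0.75 with SD 2 |
|---|---|---|
| 150/150 | 0.9015 | 0.901 |
| 155/145 | 0.901 | 0.901 |
| 160/140 | 0.900 to 0.901 | 0.900 |
| 162/138 | 0.899 to 0.900 | 0.899 |

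Ranges depend on which arm is larger.

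**5. Predictability if block sizes are known.** The expected number of seats per block that are certain in advance is b / (b/2 + 1) for even b, and 0.5 for b = 5 with a random odd seat.

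- 2/5/6: (1 + 0.5 + 1.5) / 13 = 23.1%.
- 4/6/8: (1.333 + 1.5 + 1.6) / 18 = 24.6%.

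Even blocks improve balance but not predictability. Concealment is what protects against prediction.

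**6. Blinding, side by side.** Participants are told that the trial compares a VR program with an online or mobile one. One group then receives a headset and the other a user's guide, and onboarding follows delivery. Never meeting another participant does not hide which of the two arrived. The 6.3 statement therefore cannot hold for participants, and staff who ship or onboard know the arm as well. Statistician blinding is stated consistently in 4.1 and 6.3.

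**7. Analysing by site.** The 9.4.2 test is an unstratified chi-squared test. With four equal sites and assumed PainTRAINER response rates, its power against that of a Mantel-Haenszel test stratified by site (200,000 simulated trials per pattern) is:

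- all sites 0.30: 0.904 v 0.904;
- 0.20 to 0.40: 0.884 v 0.891;
- 0.15 to 0.45: 0.859 v 0.879;
- two sites at 0.15 and two at 0.45, the most extreme pattern tried: 0.825 v 0.857.

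Unadjusted type I error was 0.038 to 0.051, so there is no inflation to correct.

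**The case against.** **Alternation.** A reader might infer that patients are simply alternated. The documents do not support that. The same sentence names a random number generator and several block sizes, and 4.1 also specifies random allocation. Garbled wording is at least as likely. What stands is that the text does not settle which sequence was used.

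**Block of 5.** A reader might infer that the scheme cannot be run or that it weakens the trial. With a random odd seat it is 1:1 in expectation, and the power cost is a fraction of a percentage point. What stands is the missing rule and the unsupported promise of equality.

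**Participant blinding.** Section 6.3 might have meant that participants are kept neutral about which program is favoured, since 4.1 plans a neutral script. That is a sound safeguard, but 6.3 says blinded to study arm, which is a different claim.

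**Statisticians.** A reader might infer that the VR-only SSQ unblinds them. That is conditional. No section says their exports carry the SSQ items, and 6.4 and 7.3 apply an SSQ+ survey in rules not limited to VR, so completion of that form need not reveal the arm. Item-level VR-only data would.

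**Timing.** The version 6.1 entry in the amendment history (August 2023) calls the study adequately powered on withdrawals to date, so much of the allocation may be done. That limits the block change but not the need to report the method or correct the blinding statement.

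**Existing safeguards.** Randomization follows consent and a completed screening week, the holder of the randomization list does not telephone participants, and usage-metadata linking lists are joined only after database lock. These reduce the risk and should be kept.

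**Conclusion.** The point holds as a contradiction in two stated bias safeguards. Participant blinding in 6.3 is incompatible with 4.1 and with what is shipped. The allocation sentence cannot ensure equality, lacks an odd-seat rule, is ambiguous about *every-other* and omits site.

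The numerical effect is small. Power stays at about 0.90 in every split in the table, and the imbalance with a random odd seat is within 10 patients in about 97% of simulated trials. These figures assume equally likely block sizes and four sites of 75. The consequences are an overstated protection from expectation bias and an allocation method that readers cannot assess. The material does not show that the trial is invalid, that allocation was in fact predictable, or that the statisticians are unblinded.

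**What to change.** **Blinding text in 6.3.** State that participants and the staff who ship and onboard are not blinded, and that statisticians are. Delete the argument that participants are less likely to guess their arm. Limit the unblinding sentence to statisticians. State whether, and how, clinical providers are kept unaware.

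**Allocation text in 6.3.** Delete *every-other*. For allocations not yet made, specify computer-generated permuted blocks of randomly varied even sizes, by site as in 4.1, with sequence and sizes concealed from recruiting and onboarding staff. The particular even sizes are a matter of preference. For participants already randomized, report the method used: block sizes, odd-seat rule, and whether by site. Say how remote enrollees and Bendcare patients, who share the UAB coordinator (5.5), are assigned to a site.

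**Statisticians' data.** Withhold item-level fields that reveal the arm (VR-only SSQ items, usage metadata, headset details from event follow-up under 8.3.4) until the primary analysis is complete. Release at database lock would be too early, because it would unblind the analysts before that analysis is run.

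**Analysis, only if allocation was by site and only before unblinding.** Use a site-stratified Mantel-Haenszel test in 9.4.2, and add site to the logistic and ANCOVA models in 9.4.2 and 9.4.3. The gain is 0 to about 2 points of power under most assumed response rates (3.2 in the most extreme pattern tried). It improves efficiency and does not correct a bias.

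**Cost.** Mostly wording, with no new data. It needs one export rule, and completeness checks on the withheld items must move to staff outside the analysis team. The site step changes the confirmatory test and uses 2 to 4 degrees of freedom in the models (three to five site strata).

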6.4 STUDY INTERVENTION COMPLIANCE

Data collection will be monitored daily by the study team. Participants will initially be sent automated reminder emails when they have not completed a survey questionnaire within a certain time frame after the original scheduled datetime. For the screener week and Week 8 daily pain journals, these reminders will occur 12 hours after and then 7 days after the original send datetime to best avoid overlapping

responses. For weekly surveys (SSQ+ to Week 8), automated reminder emails will be sent 48-hours after the original send datetime; if the participant does not respond to the first reminder, two additional 48-hr reminders will be sent. Study team members will call the participant after the third reminder if no or incomplete data are received. The participant will be asked why they missed all three reminders and be encouraged to continue to complete surveys as they are sent. If the participant continues to miss subsequent surveys, they will be sent emails containing link(s) to active and incomplete surveys or considered lost to follow-up at the discretion of the study team.

Study participants are not expected to complete 100% of surveys sent to them during the course of the study; incomplete surveys are not considered non-compliance with the protocol. In addition, surveys may be completed out of temporal order and on the same day(s)—study statisticians will determine usability of these data.

Participants who are unable to complete $\geq 80\%$ of surveys sent during any of the three months of follow-up will be ineligible for the corresponding Amazon e-gift codes (\$50 for month 1, \$225 for month 2, and \$25 for month 3, respectively).

Student interns with access only to the names and phone numbers of participants needing contact may place phone calls relating to survey compliance and return of equipment. Interns will **not** be performing activities related to recruitment or consent. If a subject has any questions outside of administrative issues, the call will be immediately transferred to a research coordinator or investigator.

6.5 CONCOMITANT THERAPY

Participants in the study can receive any ongoing treatment for their chronic pain.

7 STUDY INTERVENTION DISCONTINUATION AND PARTICIPANT DISCONTINUATION/WITHDRAWAL

7.1 DISCONTINUATION OF STUDY INTERVENTION

We do not anticipate any events that would cause the study intervention to be discontinued.

7.2 PARTICIPANT DISCONTINUATION/WITHDRAWAL FROM THE STUDY

Participants are free to withdraw from the study at any time upon request. Participants who request to withdraw will be given the option to continue completing the periodic survey questionnaires, if they choose to continue responding to surveys, they will not be withdrawn. An investigator may withdraw a participant who develops any of the exclusions criteria in section 5. the

The reason for participant discontinuation or withdrawal from the study will be recorded. Subjects who signed the informed consent form, were randomized and received the study intervention, and subsequently withdraw, or are withdrawn from the study without engaging with the study intervention (defined as any recorded VR or painTRAINER metadata by participant or self-reported usage of intervention in survey responses) will be replaced.

7.3 LOST TO FOLLOW-UP

A participant will be considered lost to follow-up if he or she fails to schedule an onboarding phone call within 30 days of device delivery or if he or she fails to complete the initial SSQ+ survey within 30 days of onboarding completion. For participants who complete the initial SSQ+ survey and fail to complete >80% of future surveys, and become unreachable by phone or email, the participant will be considered lost to follow-up 6 days following the email date of the participant's Day 60 survey.

If a participant fails to complete the weekly surveys within six days, the following actions will be taken:

- The research coordinator will attempt to contact the participant and counsel them on the importance of completing surveys and returning the equipment to be eligible for the gift card.
- Before a participant is deemed lost to follow-up, the investigator or designee will make every effort to regain contact with the participant (where possible, 3 telephone calls and, if necessary, a certified letter to the participant's last known mailing address or local equivalent methods). Contact attempts will be documented in the participant's study record.
- Should the participant continue to be unreachable, he or she will be considered to have withdrawn from the study with a primary reason of lost to follow-up.

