9.2 SAMPLE SIZE DETERMINATION

Sample Size calculations and Power Estimation

Sample Size calculations and Power Estimation

Sample Size Calculation: The primary goal of the study is to test the effectiveness of *PainTRAINER* vs. *EaseVRx*, in reducing pain intensity. The trial will be testing if there is statistical evidence that either *PainTRAINER* or *EaseVRx* is more effective in lowering average weekly pain intensity after 8 weeks from start of intervention. We estimate power to assess the effect of the

Table 1. Minimum detectable odds ratio as a function of the proportion of variability in treatment type that is explained by all other relevant covariates in the model and the baseline probability of positive treatment response.

Baseline probability	R ²			
	0.0	0.1	0.2	0.4
0.2	2.32	2.42	2.55	2.91
0.3	2.17	2.25	2.37	2.69
0.5	2.15	2.25	2.37	2.74

interventions on the treatment response (achievement of a minimally clinically important difference [MCID] of 2.0 on the NRS^{56,57} (y/n)) using logistic regression, accounting for possible confounding factors for the primary outcome described in Aim 1. The dependent variable is the treatment response and the main independent variable of interest is *PainTRAINER* vs. *EaseVRx*. **Table 1** displays the minimum odds ratio that can be detected with 90% power with the two-sided 0.05 level of significance as a function of baseline probability of positive response when a patient is treated with *EaseVRx* and R², the proportion of variability in the predictor of interest that is explained by all relevant baseline covariates in the model using data from 150 patients in the *PainTRAINER* arm and 150 in the *EaseVRx*. For example, data from 300 patients achieve 90% power to detect an odds ratio of 2.25 if the probability of positive response when a patient is treated with *PainTRAINER* is 0.3 and 0.1 of the variability in intervention is explained by all other baseline covariates in the model. These odds ratios vary between 2.15 and 2.91 and are clinically meaningful. Therefore, we have enough power to test statistical significance of predictors in the multivariable logistic regression model. Regarding clinical significance, given an MCID of 2 points on the NRS and a SD of 2 on this scale from our own digital health trials, data from 150 patients in each group

will achieve 90% power to detect a mean pain intensity score difference of 0.75, corresponding to a clinically meaningful effect size of 0.38 SD.

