9.3 POPULATIONS FOR ANALYSES

All efficacy and safety data summaries and analyses will be performed by study arm using an Intent-to-Treat (ITT) population defined as all randomized patients. The number of patients identified as candidates for the study will be reported, as will the number consented. The number and percentage of patients randomized, patient population (ITT), and treatment status (completed, discontinued/withdrew) will be summarized both by treatment group and overall. Reasons for discontinuation/withdrawal will be presented. An exploratory, per protocol (PP) analysis will focus on patients who used the assigned intervention on at least 50% of days during the first 30-day period.

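### Section 7.3 can class randomised patients as lost to follow-up before Week 8 for not scheduling a phone call, although 5.5 accepts email onboarding and one arm receives no device

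*Combined protocol and SAP*

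**What the plan says.** Sections 5.4 and 5.5 place randomisation after the screening week and before shipment, so everything below concerns patients already randomised.

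- **Onboarding (5.5).** Patients are called once the VR device or the PainTRAINER workbook has arrived. If the phone fails, staff try to schedule a call or may confirm the patient's "understanding of study procedure by email". One of these comes before the study surveys begin.
- **Loss to follow-up (7.3).** A patient is lost who "fails to schedule an onboarding phone call within 30 days of device delivery", or who does not complete the initial SSQ+ survey within 30 days of onboarding. A third rule acts six days after the Day 60 survey email. If contact is not regained, "he or she will be considered to have withdrawn from the study with a primary reason of lost to follow-up".
- **Discretion (6.4).** Patients who keep missing surveys may be considered lost by decision of the study team. No time point is given.
- **Replacement (7.2).** Randomised patients who received the intervention and then withdraw, or are "withdrawn from the study without engaging with the study intervention", are to be replaced.
- **Analysis set (9.3).** Analyses use an "Intent-to-Treat (ITT) population defined as all randomized patients".
- **Primary outcome (8.1, 9.4.2).** Daily pain is rated for seven days at baseline and again in Week 8. The primary test is a chi-squared comparison of the proportions achieving the 2-point MCID.

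**The concern.** The onboarding trigger has no email exception. Read literally, it catches the very patients for whom the email route in 5.5 exists: those who cannot be reached by phone. Its clock starts at delivery of a device, which describes the VR shipment better than a workbook. The second trigger rests on SSQ+, and the Schedule of Activities (1.3) marks the Simulator Sickness Questionnaire as VR only.

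At stake is the Week 8 pain score. An administrative rule that ends follow-up soon after randomisation leaves ITT patients with a baseline value and nothing afterwards. In a comparison where 4.1 accepts that patients cannot be blinded, a follow-up rule that can work differently in the two arms makes the completeness of the primary outcome depend on allocation.

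**Working it through.** No figure in the plan measures this, so the check sets the rules side by side and asks when each one acts.

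**1. Phone or email.** Section 5.5 accepts email confirmation as a way to start. Section 7.3 counts only a scheduled call. A patient who confirms by email on day 10 after delivery and never schedules a call satisfies 5.5 and still meets the 7.3 definition on day 30. Both cannot stand as written.

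**2. Device or workbook.** Section 5.5 names both items; 7.3 names only the device. For a PainTRAINER patient the 30-day clock has no clear start.

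**3. SSQ+.** The Schedule of Activities limits the Simulator Sickness Questionnaire to VR. Section 6.4 lists SSQ+ first in the survey series without naming an arm. The schedule also shows custom and expectation questions on Day 1 without an arm limit, so SSQ+ may be a wider form sent to everyone. The text does not settle this. If it goes to VR patients only, the second trigger has no clear meaning in the other arm.

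**4. Timing against Week 8.** Week 8 runs from Day 7 × 7 + 1 = 50 to Day 8 × 7 = 56.

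| Rule | When it acts | Before Week 8? |
|---|---|---|
| No onboarding call (7.3) | 30 days after delivery, with study surveys not yet started if onboarding is unconfirmed | Yes |
| No initial SSQ+ (7.3) | 30 days after onboarding; 30 < 50 if study days run from onboarding (assumed) | Yes |
| Day 60 rule (7.3) | Day 60 + 6 = 66 | No, 66 > 56 |
| Study team discretion (6.4) | Not stated | Can be |

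**5. What data remain.** Pain is scored only at baseline and in Week 8 (8.1), and study surveys follow confirmation of onboarding (5.5). A patient stopped at the first trigger without confirmed onboarding has no post-baseline survey of any kind. A patient onboarded by email but coded as lost would miss Week 8 if the surveys then stop. The option in 7.2 to go on answering surveys is written for patients who ask to withdraw, not for those classed as lost.

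**6. Whether the analysis closes the gap.** Section 9.4.1 does name loss to follow-up as a source of missing data. Its multiple imputation text concerns baseline covariates, and it refers missing outcomes to a repeated-measures mixed model. The primary test in 9.4.2 is a chi-squared test, and no rule says how a missing responder status enters it.

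**The case against.** The strongest reply is that 7.3 has its own safeguard. Before anyone is deemed lost, staff must make every effort to regain contact, and withdrawal is recorded only if the patient stays unreachable. A patient who answered by email has been reached. The version 6.0 entry in the amendment history gives avoiding unfair withdrawal as a reason for making the call optional, so the phone-only wording looks like a leftover. This stands in part: it makes removal possible, not certain. It does not remove the conflict. The contact steps are introduced for missed weekly surveys, not clearly for the onboarding trigger, and they name telephone calls and a certified letter but not email.

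On arms, the synopsis speaks of study devices for participants generally, and the schedule does not limit the onboarding call to VR. So a difference by arm follows from one reading of loose wording; the plan does not state it.

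A reader might infer several stronger conclusions that the documents do not support:

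- *All the rules act before Week 8.* The Day 60 rule acts afterwards.
- *Replacement removes or hides patients.* Section 7.2 adds patients and deletes none. Section 9.3 defines ITT as everyone randomised and requires treatment status by arm and reasons for withdrawal to be reported.
- *The missing-at-random assumption must fail.* Arm is known and use is recorded in program metadata. Missingness that depends on these can be missing at random if they are modelled.
- *Power falls by a calculable amount.* No loss rate is given, and replacement of patients who never engaged would largely restore the numbers.

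**Conclusion.** The concern holds as a conflict between 7.3 and 5.5 with a possible cost in primary outcome data. Two of the three triggers in 7.3, and the discretionary rule in 6.4, can end follow-up of randomised patients before Week 8. Such patients remain in the ITT set without a Week 8 pain score, possibly at different rates by arm.

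The size cannot be derived: the documents give neither the number of patients onboarded by email nor the number coded as lost at onboarding. The conclusion assumes that surveys are not started, or are stopped, once a patient is classed as lost. The plan implies this by treating the unreachable patient as withdrawn, but does not spell it out. The sample size calculation is not in question here. The point deserves an amendment because a stated rule causes the loss and the repair is cheap.

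**What to change.** 1. **Section 7.3.** Define the onboarding trigger as no call and no email confirmation within 30 days of delivery of the device or workbook, applied identically in both arms. State which arms receive SSQ+; if only one does, base the second trigger on something both arms receive.
2. **Outcome collection.** Send the Week 8 pain journals to every randomised patient who has not withdrawn consent, whatever the onboarding, engagement or loss-to-follow-up status, including patients coded under 6.4. For those with no onboarding date, anchor Week 8 to a date defined the same way in both arms, for example delivery of the device or workbook.
3. **Section 7.2.** Confirm that replaced patients remain in the ITT set, as 9.3 already implies.

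The cost is amendment wording, an anchor-date rule built into the survey schedule, and some extra automated emails to patients who did not engage. The email system already exists. Some of these patients will not reply, so the change reduces missing Week 8 scores but will not eliminate them.
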